8.12.5 Clinical Laboratory

Laboratory assessments and change from baseline will be summarized with descriptive statistics by test panel, individual laboratory test, underlying disease and group treatment group, and time point. Additionally, abnormal results including normal, abnormal clinically significant (abnormal CS), abnormal not clinically significant (abnormal NCS) captured by the eCRF will be summarized with

Statistical Analysis Plan

FK Study Identifier: SMOF-018-CP3

frequencies and percentages by clinical significance, panel, test, underlying disease group and treatment group, and time point. The denominators for percentages will be the number of patients in the analysis set for the treatment group summarized. Missing values will be presented in the summary tables. Counts and percentages of patients with shifts for the period from baseline to the end of the initial treatment phase will be summarized by analyte, underlying disease group and treatment group:

- Normal -> abnormal CS: from normal at Baseline (Day 0 or Day 1) to abnormal CS at the end of the initial treatment phase
- Normal -> abnormal NCS: from normal at Baseline to abnormal NCS at the end of the initial treatment phase
- Abnormal NCS -> abnormal CS: from abnormal NCS at Baseline to abnormal CS at the end of the initial treatment phase
- In addition, counts and percentages of patients with shifts for the period from baseline to the end of the extended treatment phase will be summarized by analyte and treatment group as described above. In this table, the denominator will be number of patients still in the study at the end of the initial treatment phase.

A data listing will display all laboratory test results and findings. A listing of lab data (including all visits) for patients who had at least one abnormal result will be provided.

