Study Day	Patients < 1500 g	Patients ≥ 1500 g
Day 1	1.0 g/kg/day	2.0 g/kg/day
Day 2	2.0 g/kg/day	3.0 g/kg/day
Day 3+	3.0 g/kg/day	3.0 g/kg/day

Investigational or control drug will be infused over 20 - 24 hours, as per hospital policy, at a weight based infusion rate. If the blood draw is from the PN/lipid infusion line, then lipid (study drug) should be held for 4 hours prior to the time of blood sampling. During study treatment, serum triglycerides (TGs) will be monitored to adjust lipid dose keeping TG levels < 250 mg/dL.

Blood samples for TG monitoring will be collected as follows:

Patients < 1500 g: At 1 g, 2 g and first dose of 3 g/kg/day

Patients ≥ 1500 g: At first dose of 3 g/kg/day

Once the target dose has been reached TGs will be assessed on a weekly basis.

Should TGs exceed 250 mg/dL, lipids will be paused until analysis of another blood sample on the following morning. If TGs are below 250 mg/dL lipids are restarted. If not this procedure has to be repeated the next morning.

Dosage of other PN components:

In addition to the study drug other macronutrients will be administered at a targeted dose as follows:

- Amino acids: 2 to 4 g/kg/day
- Dextrose: 8 to 18 mg/kg/min
- Trace elements, electrolytes, vitamins will be considered according to hospital practice and applicable guidelines.
- Use and dose of heparin and carnitine have to be documented in the concomitant mediation section in the CRF.

Route of Administration: The lipid emulsions will be infused into a central or peripheral vein

Treatment: Treatment group 1: Smoflipid 20% (investigational drug)

Clinical Study Protocol SMOF-018-CP3 Smoflipid 20% lipid injectable emulsion

Treatment group 2: Intralipid 20% (control drug)

Intravenous lipid dose management

Conjugated bilirubin levels in plasma will be assessed on a weekly basis during the initial treatment phase (visits Day 1 – Day 29) and then bi-weekly in the treatment extension phase (visits Day 36 - Day 85). If in the treatment extension phase conjugated bilirubin levels increase beyond 1.5 mg/dL, then conjugated bilirubin will be assessed weekly.

- **Lipid minimization:**

If at any point conjugated bilirubin exceeds 1.5 mg/dL (> 1.5 mg/dL), lipid dose has to be decreased to 1 g/kg/day immediately; dextrose dose should be increased accordingly to maintain adequate energy provision. Lipid dose will be maintained at 1 g/kg/d and not be increased again even if conjugated bilirubin levels decrease again below 1.5 mg/dL.

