5.3 Benefit/Risk Assessment

Study patients will receive the study drugs as part of their nutritional support for at least 28 days during their hospitalization. It is standard clinical practice to incorporate lipid emulsions into the PN protocol in patients in whom enteral or oral nutrition is not sufficient or not feasible. The alternative treatment, (i.e., supply of calories by large amounts of dextrose, or dextrose exclusively) is associated with metabolic complications and liver damage and, therefore, is not appropriate ([Koletzko, et al. 2005](#)).

In neonates, and specifically in preterm neonates, an inadequate supply of EFAs and/or their derived long-chain polyunsaturated fatty acids during the critical periods of rapid brain growth and retinal development may lead to long-term impairment of neurodevelopment and visual

Clinical Study Protocol SMOF-018-CP3 Smoflipid 20% lipid injectable emulsion

function ([Clandinin, et al. 1980, Koletzko 1992, Lapillonne 2014](#)). Essential fatty acids and polyunsaturated fatty acids cannot be synthesized from other metabolites and need to be provided to the neonates as part of their nutritional regimen. Therefore, the administration of IVLEs has to be initiated within days of birth in neonates who cannot be fed enterally ([Driscoll, et al. 2008](#)).

Both study drugs are approved in more than 60 countries. In addition, the comparator drug Intralipid is approved for use in the US. Like any other injectable lipid preparation, uncommon side effects of Smoflipid may include hypertriglyceridemia, nausea, chills, thrombocytopenia, cholestasis, and hepatic impairment after long-term treatment. However, since its introduction in 2006, no particular safety issue regarding the use of Smoflipid has been identified. In contrast, in the phase 1 study performed by Fresenius Kabi, the increase in serum triglyceride (TG) concentrations during infusion of Smoflipid was less pronounced, and elimination of TGs after the end of infusion was faster than during infusion of the standard soybean emulsion Lipovenös® 20%. This difference was probably due to the MCT portion in Smoflipid. It is expected that the fatty acid profile of Smoflipid will have a beneficial effect on the hepatic health patients compared to Intralipid ([Driscoll, et al. 2008, Rangel, et al. 2012, Vanek, et al. 2012](#)). The purpose of the present study is to confirm this beneficial effect.

6 Objectives

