12.2.4 Treatment Visits

All treatment visits should occur in a time window of ± 1 day relative to the scheduled day of

Clinical Study Protocol SMOF-018-CP3
Smoflipid 20% lipid injectable emulsion

the visit.

The following procedures will be performed at each treatment visit:

- Recording of physical examination and body measurements
 - physical examination
 - body weight
 - body length measured by a length board
 - head circumference
- Recording of vital signs
 - blood pressure
 - heart rate
 - body temperature

Additional procedures performed only on visits on Days 8, 15, 22, 43, 57 and 71:

- Collection of a blood sample for local laboratory analysis of the following parameters:
 - Biochemistry: total bilirubin, AST, ALT, GGT, ALP, TGs, creatinine, glucose, CRP
 - Hematology: CBC, leukocytes, platelets, erythrocytes, hemoglobin, hematocrit
 - Coagulation: INR
- Collection of a blood sample for central laboratory analysis of conjugated bilirubin

Additional procedures only performed on visit on Day 57:

- Collection of a blood sample for the specialized lab analyses (fatty acids, sterols and α -tocopherol)

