12.3.2 Laboratory Variables

12.3.2.1 Standard Laboratory Values Including Conjugated Bilirubin

Determination of the standard laboratory values will be assessed using established validated techniques at the local laboratory of the site except for **plasma conjugated bilirubin** which **will be assessed using established validated techniques at the central laboratory**:

The following parameters will be assessed at the local laboratory:

Biochemistry: total bilirubin, AST, ALT, GGT, ALP, TGs, creatinine, glucose, CRP

Clinical Study Protocol SMOF-018-CP3 **Smoflipid 20% lipid injectable emulsion**

Hematology: CBC (total white blood cells, total red blood cells, hemoglobin, hematocrit, mean corpuscular volume, mean corpuscular hemoglobin, mean corpuscular hemoglobin concentration, red blood cell distribution width and platelets)

Coagulation: INR

The valid normal ranges and a certification from the local laboratory will be obtained before start of the study.

The blood samples needed for the assessment of conjugated bilirubin at the central laboratory will be obtained at the same time as the blood sample for the local laboratory, to reduce the number of needle pricks. 1ml of full blood will be required for the analysis.

An exact description of the methodology for drawing, handling and shipping of the samples as well as the methodology used for the analysis of conjugated bilirubin at the central lab is outlined in the lab manual.

The investigators must review all laboratory results. Laboratory values outside the normal ranges must be assessed concerning their clinical significance by the respective investigator and the assessment must be documented on the lab report / in the patient's medical file. If the out of range value is considered clinically significant then it is an AE (see Section 13) and must be documented in the eCRF (see Section 12.4.1).

Assessments are preferably done at each visit. If the blood draw is from the PN/lipid infusion line, then lipid (study drug) should be held for 4 hours prior to the time of blood sampling. Study investigators must draw additional blood samples to monitor TG levels during initial increase in lipid dose and if TG increases beyond 250 mg/dL. The Investigators must also draw blood samples for blood cultures if a patient shows clinical symptoms of a bloodstream infection.

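### Laboratory abnormality and shift tables carry no direction, so low and high glucose, platelets, leukocytes and hemoglobin are pooled and a one-sided excess is diluted

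*SAP*

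**What the plan says.** SAP 8.12.5 (Clinical Laboratory) has two layers. First, values and change from baseline are summarized per test, underlying disease group, treatment group and time point. Under SAP 7 and 7.9 this means n, mean, standard deviation, median, minimum and maximum.

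Second, it adds frequencies of "abnormal results including normal, abnormal clinically significant (abnormal CS), abnormal not clinically significant (abnormal NCS) captured by the eCRF". Three shifts are defined:

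- "from normal at Baseline (Day 0 or Day 1) to abnormal CS at the end of the initial treatment phase"
- "from normal at Baseline to abnormal NCS at the end of the initial treatment phase"
- "from abnormal NCS at Baseline to abnormal CS at the end of the initial treatment phase"

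The extension-phase shifts follow the same scheme. Neither the section nor the titles of Tables 14.3.4.3, 14.3.4.4a/b, 14.3.4.7 and 14.3.4.8a/b mention low or high.

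Under Protocol 12.3.2.1 the clinical significance label is the investigator's judgement on any value outside the normal range, on either side. The same section states that "The valid normal ranges and a certification from the local laboratory will be obtained before start of the study".

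The panel contains analytes with two clinically distinct directions. Protocol 12.2.4 lists "Hematology: CBC, leukocytes, platelets, erythrocytes, hemoglobin, hematocrit", and glucose is in the biochemistry panel. Blood glucose is also a named secondary safety variable (SAP 5.2.2).

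**The concern.** For a two-sided analyte, the percentage abnormal mixes two different findings. Two places in the protocol give a reason to want one direction counted separately.

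- **Platelets.** Protocol 5.3 says that "uncommon side effects of Smoflipid may include hypertriglyceridemia, nausea, chills, thrombocytopenia, cholestasis, and hepatic impairment after long-term treatment". The finding to count is a low platelet count, yet the abnormality table adds high counts to it.
- **Glucose.** When lipid is minimized for raised conjugated bilirubin, Protocol 1 (Study Outline) says that "dextrose dose should be increased accordingly to maintain adequate energy provision". An arm with more minimization could plausibly show more high glucose, yet the table adds low glucose to it.

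The shift tables share the problem and have a further hole. A patient who moves from abnormal low to abnormal high, or the reverse, with the same significance label fits none of the three listed shifts.

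The SAP handles growth differently. SAP 8.11.1 classifies Z-scores as low for age, normal or high for age. At stake is how well a reader of the safety tables can see a one-sided excess, since no tests are planned and the displays are all the reader has.

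**Working it through.** The documents give no laboratory counts, so there is no figure of the plan to reproduce. What follows illustrates the mechanism with assumed counts.

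**Inputs.** SAP 8.8 reports 152 randomized patients at the interim analysis, and allocation is 1:1 (Protocol 7.3). I assume 152/2 = 76 per arm. All counts of low and high results are assumed.

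**Formula.** Risk difference d = p_A - p_B with Wald 95% CI d ± 1.96·√[p_A(1-p_A)/76 + p_B(1-p_B)/76].

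**Step 1: direction shown.** Low values in 8/76 versus 1/76, that is 10.5% versus 1.3%. d = 9.2 points, SE 3.76, CI 1.9 to 16.6. The ratio is 8/1 = 8.0.

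**Step 2: the same low counts after pooling with high values.**

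| High values, A / B | Pooled, A vs B | Difference (95% CI), points | Ratio |
|---|---|---|---|
| 4 / 4 (balanced) | 12/76 vs 5/76 | 9.2 (-0.7 to 19.1) | 2.4 |
| 2 / 5 (partly opposite) | 10/76 vs 6/76 | 5.3 (-4.5 to 15.0) | 1.7 |
| 1 / 8 (mirror image) | 9/76 vs 9/76 | 0.0 (-10.3 to 10.3) | 1.0 |

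Balanced high values leave the absolute difference alone but widen the interval and shrink the ratio. Opposite high values shrink the difference itself. Only the mirror image removes it.

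**Step 3: would the means show it?** Suppose the mirror-image counts came from a pure shift of a normal distribution. The implied mean difference is z(8/76) - z(1/76) = -1.252 - (-2.222) = 0.97 SD. With SE √(2/76) = 0.162, the approximate 95% CI is 0.65 to 1.29 SD. Assumed mirror-image tail rates of 10%/2%, 15%/5% and 20%/5% imply 0.77, 0.61 and 0.80 SD. The planned value and change-from-baseline tables would show shifts of that size.

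**Step 4: what remains uncovered.** The continuous summaries do not count patients, and the minimum and maximum each reflect a single value. An excess confined to a few patients in one tail can leave the mean and median nearly unchanged. On the adverse event side, Protocol 12.3.2.1 makes every clinically significant value an adverse event. Protocol Table 3 (13.2.1) also sends grade 3 values to adverse events and grade 4 values to serious adverse events. Grade 1 and 2 values judged not clinically relevant need not be recorded as adverse events. The values left with no count by direction are therefore mainly mild ones rated not clinically significant.

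**The case against.** The strongest reply is that the category tables are a supplement. The main laboratory analysis is the signed summary of values and changes, which includes every result whatever its significance label. The more serious abnormalities reach the adverse event tables, where they appear by preferred term and severity. This stands, and it limits the point. A reader might infer that direction is lost for results rated not clinically significant, or from the laboratory analysis as a whole. The documents do not support that.

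A reader might also infer that opposite signals are likely to cancel between arms. They do not support that either. Protocol 5.3 describes thrombocytopenia as a possible effect of injectable lipids generally and suggests no excess of high platelets in the other arm. The dextrose rule points to higher glucose only, which by itself would raise that arm's pooled abnormal percentage. The realistic problem is dilution.

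Three further replies have weight. The trial's main laboratory question is hepatic, where elevation is the concern and pooling matters little. Of the four two-sided analytes named here, only glucose is a listed secondary variable. The table shells and the eCRF are separate documents that were not available, so a low/high split in them cannot be excluded.

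What these replies leave untouched is that the SAP text specifies no count of patients below or above range. The listings are a weak substitute, because a reader would have to do the counting. Moreover, SAP 8.12.5 promises a listing of all laboratory results, but SAP Section 10 contains no such title.

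**Conclusion.** The point holds as a minor weakness of presentation. The abnormality and shift categories in SAP 8.12.5 pool low and high results, and for two-sided analytes a one-sided excess is diluted in those tables. In the illustration, a ratio of 8.0 falls to 2.4 with balanced opposite abnormalities, and the difference falls from 9.2 to 5.3 points with partly opposite ones. It reaches zero only in the mirror-image case.

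These sizes rest on assumed counts and an assumed 76 per arm; they show the mechanism and predict nothing about this trial. The SAP reports no p-values, and no decision or error rate depends on these tables. Provided raw values and ranges are kept, the split can still be derived. The conclusion also assumes that the unseen table shells follow the SAP text.

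**What to change.** In SAP 8.12.5, classify each result for two-sided analytes (at least glucose, platelets, leukocytes and hemoglobin) as low, normal or high against the local laboratory's range, and keep the CS/NCS label alongside. Present the by-visit tables by direction, and define shifts as normal to low, normal to high, low to high and high to low, each with its CS/NCS label. Analytes where only elevation is of concern can keep the present layout. Bring the shells for Tables 14.3.4.3, 14.3.4.4a/b, 14.3.4.7 and 14.3.4.8a/b into line. If they already split by direction, one sentence in the SAP is enough.

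The cost is programming and additional table rows. No new blood samples or measurements are needed, since results are already recorded and local ranges are obtained under Protocol 12.3.2.1. The documents do not say whether those ranges are held electronically with the results; if they are not, they would have to be entered for the 15 centers.

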8.12.6 Vital Signs

Vital sign measurements and change from baseline of vital signs (including heart rate, temperature, systolic and diastolic blood pressure) will be summarized with descriptive statistics by underlying disease group, treatment group, and time point. A data listing of all data will also be included.

8.12.7 Physical Examinations

Physical examinations will be summarized by assessment, body system, underlying disease group and treatment group using number and percentage of patients in each assessment category (i.e., normal, abnormal NCS, and abnormal CS). Denominators for the percentages will be based on the number of patients within the treatment group for the assessment summarized. In addition, counts and percentages of patients with shifts will be summarized by body system and treatment group (see laboratory data above). Denominators for the percentages will be based on the number of patients with a body system evaluation at both baseline and end of study in each treatment group.

A data listing of physical examination data will be generated by patient.

8.13 Analysis of Nutritional Intake

The calories per kg of body weight and day and the percentage of calories provided as enteral, oral, parenteral (including study drug) and study drug relative to total calories will be summarized by underlying disease and treatment group for each study week and the overall treatment period.

For enteral and parenteral nutrition components, the protein, fat and carbohydrate intake will be calculated based on the product information. For example, the protein intake from enteral nutrition (EN) for a patient will be computed according to

$$\text{Protein intake [g/kg/day]} = \frac{\text{EN intake [kcal/kg/day]} \cdot \text{g Protein per 100 kcal}^1}{100}$$

Calculations for fat and carbohydrates and PN products will be performed analogously.

All information regarding the exposure to other nutrition, (i.e., oral, enteral and non-nutritional sources) will be listed. This includes the item/product, dosage/amount and (estimated) calories.

¹ Protein contents per 100 kcal are based on product information.

Statistical Analysis Plan

FK Study Identifier: SMOF-018-CP3

